Sample Size Computations and Assumptions

The primary outcome measures are EPC-2, EPC -3, EPC -4, EPC -7, and EPC -8. Also, there are many secondary outcome measures. Based on our pilot study, mean and SD (standard deviation) are reported below.

	EPC-2	EPC-3	EPC-4	EPC-7	EPC-8
Mean	0.675783	0.016016	0.050813	0.297092	0.631728
SD	0.702561	0.010805	0.056709	0.412414	0.691299

This is a longitudinal study and primary observations will be made at baseline, 6 weeks and 12 weeks follow-ups. Due to 5 primary outcome measures, we adjusted alpha=0.01 (=0.05/5). Due to multiple sub-studies, we plan to enroll a large evaluable cohort of size n=240. With a correlation of 0.5 on any two consecutive time-point measures, (this is a conservative estimate) and n1=120, n=120 at alpha= 0.01 and power=0.90, we can detect the effect size of 0.5 SD using a two sample t-test in a longitudinal setting. The detectable effects for each EPC is given below.

Power	Correlation	EPC-2	EPC-3	EPC-4	EPC-7	EPC-8
80%	0.50	0.351	0.005	0.028	0.206	0.346
90%	0.50	0.223	0.003	0.018	0.131	0.219
80%	0.80	0.197	0.003	0.016	0.116	0.194
90%	0.80	0.156	0.002	0.013	0.092	0.153

To adjust for attrition/drop out we have increased the sample size to 400.

Associations of PM_{2.5} exposures with measured outcomes will be estimated using mixed effects models. We will use interaction variables to detect whether the association between PM_{2.5} and outcomes is significantly different between with or without carnosine groups. We will perform a formal mediation analysis, which allows for interactions to determine the degree to which carnosine levels mediate the effect of PM_{2.5} on our outcomes. Plots of subject-specific differences over pollution concentrations along with regression plots will be generated.

Sample Size Recommendation

Sample size of 240 participants (120 carnosine supplementation, 120 placebo group) provides sufficient sample size for the primary endpoint as well as other secondary endpoints.

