Due to the prolonged intervention period (12 weeks), two follow-up visits and the inconvenience of taking multiple oral capsules daily, we anticipate a 40% attrition from screening (Visit # 1) through 12-week follow-up (Visit # 4). Therefore, we have established a goal of stratified identification of a total of 400 participants (1:1) at screening (Visit # 1). We anticipate that with a conservative estimate of 60% retention, 120 participants in each group (supplementation, placebo) will complete the entire study.

Multiple Testing Issue

Type I error correction in the context of an early phase clinical trial that performs multiple tests can serve to protect the study interpretation against Type I error inflation. However, the use of corrections for multiple comparisons in “proof-of-concept-studies” is problematic. At this investigational level, tight control of the overall family-wise Type I error rate would increase the likelihood that the investigators would miss a finding of potential importance by attributing it to chance simply because the p-value is large. The study investigators have, in this protocol, attempted to balance the need to control the number of evaluations with the need to identify new effects by not incorporating a multiplicity correction. The primary outcomes measures will be declared significant for alpha <0.01. There will not be any adjustments for secondary outcome measures and will be declared significant at alpha <0.05.

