There are 5 primary endpoints: difference in EPCs (EPC-2, EPC-3, EPC-4, EPC-7, and EPC-8) between Carnosine and placebo groups at 6 weeks and 12 weeks. These endpoints will be evaluated at the alpha=0.01. There are four secondary endpoints: difference in EPCs between Carnosine and placebo groups at 12 weeks, difference in EPCs between Carnosine and placebo groups at 6 weeks, difference in arterial stiffness between carnosine and placebo groups at 6 and 12 weeks, difference in endothelial microparticles between carnosine and placebo groups at 6 and 12 weeks, and difference in platelet monocyte aggregates between carnosine and placebo groups at 6 and 12 weeks.

Continuous variables will be presented by summary statistics (such as mean, median, standard error, range, 95% CI, correlations) and the categorical variables by frequency distributions (frequency counts, percentages and 95% CI). We will also calculate correlations along with confidence intervals. To identify significant differences due to intervention, we will compare the differences using a two sample t-test. We will use regression (logistic or linear) to model and test the effect of other covariates such as age and race. We also will compare outcome measures using GLM and MIXED model procedures to account of repeat observations. General statistical analyses will be performed with the SAS statistical software package (SAS Institute Inc., Cary, NC).

Statistical Monitoring Rule

[figure not shown]
Safety monitoring of the accumulated outcomes data is designed to ensure the continuing safety of the currently enrolled participants and participants not yet enrolled. This is achieved by stopping the trial early to reduce the number of participants exposed to a harmful or ineffective supplementation.

Monitoring Non-efficacious Supplementation (Futility)

We do not plan any interim analyses for futility due to longer follow-up (1 year).

Monitoring Toxic Supplementation (Safety)

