In this study, no adjustments have been made for multiple comparisons. Measures of effect will be effect size, the standard error of the effect size, the 95% confidence interval for the effect size and the *p*-value. *P*-values will be interpreted at nominal 0.05 levels.

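### The primary EPCs are tested at 0.01 in Section 8 and in the Section 15 outcome analyses, but Multiple Comparisons reads p-values at 0.05 and gives 95% intervals for every effect, so test and interval can disagree

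*Combined protocol and SAP*

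**What the plan says.** Three places set the primary level at 0.01:

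- Section 8, Sample Size Computations and Assumptions: "Due to 5 primary outcome measures, we adjusted alpha=0.01 (=0.05/5".
- Section 8, Multiple Testing Issue: "The primary outcomes measures will be declared significant for alpha <0.01". For secondary outcomes the same paragraph adds: "There will not be any adjustments for secondary outcome measures and will be declared significant at alpha <0.05".
- Section 15, Outcome Analyses, on the five EPC endpoints: "These endpoints will be evaluated at the alpha=0.01".

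The Multiple Comparisons paragraph that closes Section 15 says otherwise. It opens with "In this study, no adjustments have been made for multiple comparisons", lists the effect size, "the standard error of the effect size, the 95% confidence interval for the effect size" and the p-value as the measures to be reported, and says of p-values that these "values will be interpreted at nominal 0.05 levels". It makes no exception for the primary EPCs.

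A 95% interval is also named in Outcome Analyses, among descriptive summaries: "Continuous variables will be presented by summary statistics (such as mean, median, standard error, range, 95% CI, correlations". No 99% interval appears in the document, and nothing says how the reported interval relates to the 0.01 decision.

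The set of primary contrasts is also unclear. Outcome Analyses counts EPC differences at 6 and 12 weeks as primary, then lists EPC differences at 12 weeks and at 6 weeks again among the secondary endpoints. The Executive Summary also lists the 12-week EPC difference as secondary.

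**The concern.** A 95% interval is the companion of a two-sided 0.05 test. If the primary decision is taken at 0.01, any EPC with p between 0.01 and 0.05 fails the test but has a reported interval clear of zero. The report would then carry two readings of one primary result, and the plan does not say which governs.

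The interval level follows from a conflict that the plan leaves open: 0.01 in three places, and an unadjusted 0.05 in Multiple Comparisons. It still needs its own edit. Changing only the p-value sentence to 0.01 would leave the interval sentence as it is, and the primary intervals would no longer match the test. Settling this before unblinding removes the option of choosing between p-value and interval once the results are known.

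**Working it through.** **Inputs.** Five primary EPCs; alpha 0.01 each; 120 evaluable per arm; design effect 0.5 SD; power 0.90; two-sample t-test; pilot SD for EPC-2 of 0.702561 (all Section 8). The plan does not state sidedness. Two-sided is assumed, and it reproduces the planned size.

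**The plan's own figures.** 0.05/5 = 0.01. Normal formula: n per arm = 2(z₀.₉₉₅ + z₀.₉₀)²/0.5² = 2(2.576 + 1.282)²/0.25 ≈ 119.1, rounded up to 120. Power at 120 per arm from the noncentral t is 0.898. With a correlation of 0.5, the SD of a change score equals the SD of a single value, because √(2(1 − 0.5)) = 1, so post-value and change-score calculations agree. The text's 90% power at 0.5 SD therefore rests on two-sided 0.01. This concerns the figure in the text, not the detectable-effect table below it.

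**Where test and interval part.** SE of the difference in SD units = √(2/120) = 0.1291, with 238 df.

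- 95% interval excludes zero when the observed difference exceeds 1.970 × 0.1291 = 0.254 SD.
- p falls below 0.01 when it exceeds 2.597 × 0.1291 = 0.335 SD.
- Disagreement zone: 0.254 to 0.335 SD. For EPC-2, multiplying by 0.7026, about 0.179 to 0.236.
- Width ratio, 99% to 95%: 2.597/1.970 = 1.32.

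**Example.** Observed difference 0.30 SD: t = 0.30/0.1291 = 2.32, p = 0.021. The 95% interval is 0.046 to 0.554 and excludes zero; the 99% interval is −0.035 to 0.635 and includes it.

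**How often, per EPC.** P(0.01 < p ≤ 0.05) = power at 0.05 minus power at 0.01, from the noncentral t with 238 df and noncentrality d√(120/2).

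| True difference (SD) | Power at 0.05 | Power at 0.01 | Disagreement |
|---|---|---|---|
| 0 | 0.050 | 0.010 | 4.0% |
| 0.2 | 0.339 | 0.150 | 18.9% |
| 0.3 | 0.639 | 0.394 | 24.4% |
| 0.4 | 0.870 | 0.692 | 17.8% |
| 0.5 | 0.971 | 0.898 | 7.3% |

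**At least one of five, no effect, one comparison per EPC.** If independent: 1 − 0.96⁵ = 18.5%. The document gives no correlation between EPCs, so a range is assumed. Simulation with equally correlated normal statistics (400,000 draws) gives about 16% at 0.5 and about 12% at 0.8. If 6 and 12 weeks both count, there are ten comparisons, and independence would give 1 − 0.96¹⁰ = 33.5%. That is an illustration only, since the plan itself assumes a correlation of 0.5 between consecutive time points.

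**The case against.** The strongest reply is that the plan has no single rule for the interval to contradict. Within Multiple Comparisons, the 95% interval and the 0.05 level agree with each other, and Multiple Testing Issue also speaks of forgoing a multiplicity correction before it sets 0.01. On this view the defect is the unresolved alpha, and the interval is one line of its repair. That is right about the root. The interval sentence must still be edited if the conflict is settled at 0.01, the level stated specifically for the EPCs and used for the sample size.

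A second reply also stands in part: a 95% interval beside a stricter test is not an error if it is labelled as unadjusted. This plan has no such label.

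Third, some of these EPC contrasts are also listed as secondary, where 0.05 and a 95% interval match. That is true, and it means the repair must say which contrasts are primary.

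Three stronger readings are tempting but unsupported:

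- That the intervals *will* exclude zero for non-significant EPCs. This needs p between 0.01 and 0.05. The 24% is near the peak; at the planned 0.5 SD it is 7%.
- That the 95% interval undoes the correction for five outcomes. No section lets the interval decide significance, so the type I error of the 0.01 test is unchanged. The 22.6% chance of at least one false positive (1 − 0.95⁵, against 1 − 0.99⁵ = 4.9%) is the cost of *testing* at 0.05, and it assumes five independent endpoints. These are cell subsets gated from the same blood sample.
- That every 95% interval in Section 15 is at fault. Those in Outcome Analyses sit beside the mean, median and range and are descriptive.

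**Conclusion.** The point holds in a limited form. The document gives two levels for the primary EPCs, and its only stated confidence level matches the one that the sample size was not built on. If 0.01 governs, a primary EPC with an observed difference of about 0.254 to 0.335 SD would be declared not significant beside a 95% interval that excludes zero. If 0.05 governs, interval and test agree, but the Bonferroni level used for sizing has been dropped.

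The disagreement rates in the working assume 120 evaluable per arm, equal SDs, two-sided t-tests and one comparison per EPC. The any-of-five figures also depend on the assumed correlation between EPCs. This is an ambiguity in decision and reporting that should be settled before unblinding. It does not affect the sample size.

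**What to change.** In Section 15, Multiple Comparisons:

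1. Except the primary EPCs from the no-adjustment and nominal 0.05 sentences, and state 0.01 for them. Bring the no-correction wording in Section 8, Multiple Testing Issue, into line.
2. Report 99% confidence intervals for the primary EPC arm differences, and 95% intervals for secondary and exploratory effects. If the per-test level changes, the interval level changes with it.
3. State which EPC contrasts (6 weeks, 12 weeks or both) are primary, and remove them from the secondary list in Outcome Analyses and, where it applies, the Executive Summary.

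An acceptable alternative to item 2 is to keep 95% intervals for the primary EPCs and label them as unadjusted and not deciding significance. The descriptive 95% intervals in Outcome Analyses can stay.

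The cost is a few sentences. With 99% intervals, the primary intervals become about 1.32 times as wide; the sample size does not change.

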16. TRIAL MANAGEMENT

Institutional Review Board (IRB) AND Informed Consent

This protocol and the informed consent document and any subsequent modifications will be reviewed and approved by the IRB or ethics committee responsible for oversight of the study. A signed consent form will be obtained from the participant. The consent form will describe the purpose of the study, the procedures to be followed, and the risks and benefits of participation. A copy of the consent form will be given to the subject and this fact will be documented in the participant's medical record if recruited from a clinic.

Informed Consent Process

Potential participants will be approached by one of the study investigators or research coordinators. Information regarding study participation will be provided to the potential participant. The informed consent includes descriptions of all study related procedures, all possible risks to participant, and the time commitment involved with participating. All consent forms will have IRB approval. Individuals who agree to participate will receive a copy of the signed informed consent. The research staff member obtaining consent will document the informed process in the participant's chart if recruited from a clinic.

Risks Associated with Manufacturing and Consuming of Dietary Supplement

Manufacturing Dietary Supplement

Supplement manufacturing is done under strict sterile conditions; however, there is a rare chance that the capsules could become contaminated while being processed. Quality control checks will be done on the manufacturing process, and if the tests reveal break in protocol or contamination, the participant will be notified and instructed on whether or not he/she should be treated with antibiotics. The participant will be diligently assessed for adverse reactions or events at each follow-up visit (Visit # 3 and Visit # 4). If the participant notes a fever, he/she will be requested to notify the investigator/study team immediately.

Consuming Dietary Supplement

Possible risks of Carnosine supplementation include: tingling of upper / lower extremities, drop in blood pressure, nausea, vomiting, stomach upset.

Participants who are taking antihypertension medications at the time of the study may be susceptible to a temporary sudden drop in blood pressure; during which time the participant may be at an increased risk of stroke and heart attack. The participant will be advised to inform the research team immediately of any symptoms of dizziness, light-headedness, chest pain, chest tightening, nausea, blurred vision, slurred speech, facial drooping, decrease sensations anywhere on your body, or weakness or a decrease in strength of the arms or legs. The participant will be closely monitored if started back on the study supplement regimen. The study physician will conduct a detailed assessment and provide its recommendations to the PI.

Adequacy of Protection Against Risks

The precautionary measures mentioned in the last two sections will minimize the risk associated with taking study dietary supplement. Overall the study procedures are low risk and in previous similar trials there was no complications related to Carnosine or placebo supplementation in healthy participants.^{34, 37}

Potential Benefits of the Proposed Research to the Participants and Others

The potential benefits of this research for participants include reduced oxidative stress from PM_{2.5} pollution which will have therapeutic effects such as decrease in CVD progression and ultimately decreased CVD mortality. This project will also provide mechanistic insight into Carnosine supplementation which will be useful for finding new treatments for other diseases.

Risk Benefit Analysis

The supplementation of dietary Carnosine offers a new option to participants with existing CVD of different intensities. The goal of this supplementation is to improve ameliorate the progressive nature of CVD by facilitating the reduction of oxidative stress on vasculature. Having highly trained experts oversee the supplementation with close study monitoring substantially reduces the likelihood of AEs. The potential risks to the participants remain reasonably low in relation to the possible benefit of improving their CVD risk factors during high pollution season, without the involvement of prescription medications or invasive diagnostic / treatment procedures.

Importance of Knowledge to be Gained

The knowledge to be gained from this clinical trial is significant in that 1) participants with high exposure to PM_{2.5} environmental pollution and related CVD risk factors may benefit from receiving a freely available over the counter dietary supplement that heretofore has demonstrated few risks to the participant.

The study has been designed to address critical limitations in the previous published studies which have not looked at the effect of Carnosine supplementation on mitigating CVD risk factors. The risks to the participants are reasonable in relation to the knowledge gained from this study since this supplementation therapy may potentially reduce the widely prevalent and debilitating effects of PM_{2.5} pollution.

Data Safety Monitoring Board (DSMB)

The Data and Safety Monitoring Plan has been outlined in Section 16 above.

Clinical Recruitment

The PI and other involved investigators will oversee that the clinical research team and investigators are trained on but not limited to the following topics:

1. Maintaining IRB required trainings and certifications (e.g. CITI program, etc.)
2. Obtaining informed consent
3. High quality data collection
4. Good clinical practice
5. HIPAA privacy
6. Institutional compliance
7. Understanding the nature of the protocol or investigational plan.

8. The study PI understands and accepts his or her obligation to obtain IRB review and approval of a clinical investigation before the investigation may be initiated and to ensure continuing review of the study by the IRB in accordance with 21 CFR Part 56, and to keep the sponsor informed of such IRB approval and subsequent IRB actions concerning the study.
9. Access to an adequate number of suitable potential candidates / participants to conduct the investigation.
10. Adequate facilities for supplement preparation and conducting the clinical investigation.
11. Sufficient time to carry out the responsibilities of best practices of clinical research
12. The PI understands periodic / random audits by the IRB may occur

Database

The Envirome Institute will maintain a study database in a web-accessible electronic format. Detailed documentation of study variables will be prepared and available to study Investigators, and where necessary, to external scientists. Appropriate confidentiality and security of these files will be maintained at all times.

Security

Several levels of security will be implemented to protect the confidentiality of the data. All authorized users will be provided a unique name/password and will be given access as identified by the Principal Investigator. Data will be stored on a REDCap database which is HIPAA compliant database routinely utilized by clinical scientists nationwide to store sensitive research data.

Data Quality

All data will have to pass through range and logical checks in addition to intra- and inter-form checks for consistency. The sequence of events will be enforced by allowing subordinate forms to become accessible only after its primary form has been submitted. If a response to a question on a form requires ancillary forms to be completed, the user will receive reminder messages within the application to complete the proper form. Regular reports on the REDCap data entry and completeness will be generated. Data quality or management questions or concerns will be immediately addressed.

Dissemination

The overall usefulness of scientific research depends not only on the importance of the findings, but also on its eventual reach and effect on population health. Therefore, research projects must integrate ways to promote the eventual diffusion of the results into their research plans. The Envirome Institute will work with professional associations like the NIH, NIEHS, American Heart Association for a number of initiatives including cardiovascular diseases and environmental pollution. The Envirome Institute will use multiple general dissemination methods that will be

[figure not shown]
tailored for the target audiences (e.g. manuscripts, presentations, television, multimedia, social media).

18. TABLES

TABLE 1: Screening and Enrollment Timeline of NEAT Clinical Trial for Year # 1 (2020)

Jan	Feb	Mar	Apr	May	Jun	Jul	Aug	Sep			
Potential Candidates Identification											
	Clinical Screening (Visit # 1)										
	Select Eligible Candidates from Visit # 1										
				Supplement Intervention Period (Total 12 weeks per Participant)							
				Baseline Assessment (Visit #2) Start Supplement							
					Follow-Up # 1 at 6 weeks (Visit # 3)						
						Follow-Up # 2 at 12 weeks (Visit # 4)					

TABLE 2: Screening and Enrollment Timeline of NEAT Clinical Trial for Year # 2 (2021)

Jan	Feb	Mar	Apr	May	Jun	Jul	Aug	Sep			
Potential Candidates Identification											
	Clinical Screening (Visit # 1)										
	Select Eligible Candidates from Visit # 1										
				Supplement Intervention Period (Total 12 weeks per Participant)							
				Baseline Assessment (Visit #2) Start Supplement							
					Follow-Up # 1 at 6 weeks (Visit # 3)						
						Follow-Up # 2 at 12 weeks (Visit # 4)					

[figure not shown]

Table 3: Schedule of Procedures At Each Visit / Encounter

Study Activities	Visit # 1 (Screening)	Visit # 2 (Baseline Assessment)	Visit # 3 (Follow-Up # 1)	Visit # 4 (Follow-Up # 2)	4-12 Month Safety Check
Informed Consent	X				
Contact & Demographics	X	X	X	X	
Medical History		X	X	X	X
Sleep / Dietary / Social / Exposure Questionnaires		X	X	X	
Blood & Urine Samples	X (Urine only)	X	X	X	
Physical Exam		X	X	X	
Arterial Stiffness Exam		X	X	X	
Physical Function Exam		X	X	X	
Supplement Distribution		X	X		
Checkout (Payment)	X (\$25)	X (\$50)	X (\$75)	X (\$100)	
Adverse Events Check			X	X	X

Table 4: Study Visit Components' Time Requirements

Study Activities	Visit # 1 (Screening)	Visit # 2 (Baseline Assessment)	Visit # 3 (Follow-Up # 1)	Visit # 4 (Follow-Up # 2)	4-12 Month Safety Check
Informed Consent	30 mins				
Contact & Demographics	5 mins				
Medical History		30 mins	15 mins	15 mins	2 mins
Sleep / Dietary / Social / Exposure Questionnaires					
Blood & Urine Samples	10 min (Urine only)	15 mins	15 mins	15 mins	
Physical Exam		10 mins	5 mins	5 mins	
Arterial Stiffness Exam		20 mins	20 mins	20 mins	
Physical Function Exam		20 mins	20 mins	20 mins	
Supplement Distribution		10 mins	10 mins		
Checkout	10 mins	10 mins	10 mins	10 mins	
Adverse Events Check			5 mins	5 mins	2 mins
Estimated Visit Time	60 mins	120 mins	100 mins	100 mins	5 mins

